### 4.2 Exclusion Criteria

- 4.2.1 Inability to abstain from NSAID (including aspirin) and selective COX-2 inhibitor therapy at the time of randomization through the completion of the study (the study period is defined as baseline to exit endoscopy at 18 months after randomization which defines the completion of the study). Participants may take Tylenol and Non-NSAID pain relievers.
- 4.2.2 Current or planned use of anticoagulant drugs such as: warfarin, heparin, low molecular weight heparin, Plavix, or Aggrenox throughout the course of the study.
- 4.2.3 Individuals taking the drugs listed below may not be randomized unless they are willing to stop the medications (and possibly change to alternative non-excluded medications to

treat the same conditions) no less than 1 month prior to starting aspirin or placebo on this study. Consultation with the participant's primary care provider will be obtained prior to stopping any agent. The use of the following drugs or drug classes is prohibited during aspirin/placebo treatment:

NSAIDs: such as aspirin, Naprosyn, ketorolac and others NSAIDs

COX-2 inhibitors: such as Celecoxib, Rofecoxib

Valproic acid

Sulfinpyrazone

Probenecid

Corticosteroids (other than short-term use defined as less than 2 weeks or prn use of an inhaler less than twice per month)

Platelet aggregation inhibitors, except in a monitored antithrombotic regimen

Methotrexate (MTX)

Vaccines containing live viruses

Ginkgo

- 4.2.4 Individuals with uncontrolled renal insufficiency or renal failure.
- 4.2.5 Participants with fundoplication within the past year, bariatric surgery or any other major upper GI surgery. Fundoplication more than one year ago will not be grounds for exclusion. Cholecystectomy will not be grounds for exclusion.
- 4.2.6 History of invasive cancer diagnosis  $\leq$  12 months prior to randomization, excepting non-melanoma skin cancer. Patients with T1a adenocarcinoma of the esophagus arising in the setting of Barrett's esophagus are eligible for enrollment in the trial.
- 4.2.7 History of cancer treatment  $\leq$  12 months prior to randomization, excepting hormonal therapy (except treatment for non-melanoma skin cancer or carcinoma-in-situ of the cervix).
- 4.2.8 Receipt of any other investigational agents  $\leq$  3 months prior to randomization, except innocuous agents with no known interaction with the study agents (e.g., standard dose multivitamins or topical agents for limited skin conditions), at the discretion of the Protocol Lead Investigator at each Participating Site.
- 4.2.9 History of allergic reactions attributed to aspirin or compounds of similar chemical or biologic composition to the study agent.
- 4.2.10 History of endoscopically or radiographically diagnosed peptic ulcer disease with upper GI bleeding during the past 5 years or history of endoscopically or radiographically diagnosed peptic ulcer disease with upper GI bleeding any time while taking aspirin.
- 4.2.11 Uncontrolled intercurrent illness including, but not limited to: ongoing or active infection, symptomatic congestive heart failure, unstable angina pectoris, cardiac arrhythmia, bleeding disorder, vitamin K deficiency, alcohol abuse (defined as ingestion of 3 or more drinks per day) or psychiatric illness/social situations that would limit compliance with study requirements.

- 4.2.12 Pregnant women. Note: because the teratogenic or abortifacient effects of the study agents remain incompletely defined.
- 4.2.13 Breast feeding women. Note: because there is an unknown but potential risk for adverse events in nursing infants secondary to treatment of the mother with the study agents, women who are breast-feeding will be excluded.
- 4.2.14 Surveillance biopsies demonstrating residual BE at qualifying exam.
- 4.2.15 Presence of an esophageal stricture defined as “any recognizable change in esophageal luminal caliber that is accompanied by symptoms of dysphagia, or any asymptomatic narrowing that either will not allow any adult endoscope to pass or allows passage with resistance.”
- 4.2.16 Patients with human immunodeficiency virus (HIV) infection.

### **4.3 Inclusion of Women and Minorities**

Both men and women and members of all races and ethnic groups are eligible for this trial. However, BE is more common among Caucasian males and we expect our recruitment to reflect the known demographics of this condition. There is no information available regarding differential effects of the study agents in population subsets defined by race, gender, or ethnicity, and there will be no reason to expect such differences exist. Therefore, although the planned analysis will look for differences in intervention effect based on racial and gender groupings, the sample size is not increased in order to provide additional power for these subset analyses.

### **4.4 Recruitment and Retention Plan**

See Document A for details.

## **5. AGENT ADMINISTRATION**

Intervention agents will be administered on an outpatient basis. Reported adverse events and potential risks are described in Section 6.2.

### **5.1 Dose Regimen and Dose Groups**

Doses of the study agents will be either

- (a) Aspirin 325 mg PO QD or
- (b) Matching placebo PO QD

Agents will be administered for 12 months after randomization.

### **5.2 Aspirin Administration**

Aspirin or aspirin placebo will all be administered once in the morning with a meal. All study agents will be self-administered by the participants. Participants will be given sufficient agent supplies to last for a 3 month period (between phone interviews or mail contacts) plus a short time period beyond their scheduled interview to account for unavoidable scheduling delays.

*First Randomized Pill Bottle:* Participants who continue to be eligible based on qualifying endoscopy and biopsies and interested in study participation will receive a supply of study pills. The supply will be the randomly assigned study agent. Participants will be instructed to start this

new bottle immediately upon receipt and to record the date that the bottle is started. The study agent may be dispensed to the participant at the randomization visit or shipped directly to the participant.

*Subsequent Randomized Pills:* Participants will be instructed to take at least 3 months of pills from each bottle prior to starting their new one and to record the date that the new bottle is started. Bottles containing randomized pills will be mailed in approximately three month intervals adjusting for the previous pill bottle start date. Special shipments will also be made upon request, if, for example, a participant loses their bottle or does not receive their new bottle of pills.

### **5.3 Run-In Procedures**

This trial will not include a placebo or active agent run-in period

### **5.4. Contraindications**

Exclusions as outlined in Section 4.2

### **5.5 Concomitant Medications**

Concurrent use of aspirin with valproic acid has been reported to increase the plasma concentration of valproic acid and induce valproic acid toxicity (see exclusions). Concurrent use of aspirin with high-dose corticosteroids may increase the risk of gastrointestinal side effects (see exclusions). Concurrent use with platelet aggregation inhibitors is prohibited, except in a monitored antithrombotic regimen, because the risk of bleeding may be increased. Sulfapyrazone and probenecid may decrease renal clearance and increase plasma concentrations and toxicity of salicylates (see exclusions). Aspirin may block excretion of methotrexate (MTX) and increase MTX toxicity (see exclusions). No vaccines containing live viruses can be administered during the study due to an increased risk of Reye's syndrome (see exclusions). Gingko may be associated with increased risk of bleeding; patients will not be allowed to use gingko on this study. All medications (prescription and over-the-counter), vitamin and mineral supplements, and/or herbs taken by the participant will be documented on the concomitant medication CRF and will include: start and stop dates (if known; if unknown, will be marked "unknown" in the database), and dose. Medications taken for a procedure (e.g., biopsy) will also be included.

### **5.6 Dose Modification**

There will be no dose modification. Participants with Grade 4 adverse events possibly, probably or definitely related to study agent, or Grade 3 adverse events possibly, probably or definitely related to study agent will be taken off study and followed off study agent for at least 30 days or for the remainder of the planned intervention period (whichever is longer). Participants with Grade 2 adverse events possibly, probably or definitely related to the study agent can be taken off study agent for up to 1 week. If the adverse event resolves, the study agent may be resumed. If the adverse event continues, participants will be taken off study. Participants with any Grade 1 adverse event may continue the study agent at full dose, unless either the participant or the investigator finds the adverse event to be intolerable. In this instance, the study agent can be stopped and restarted as described for participants with Grade 2 adverse events. Rechallenge of participants who experience Grade 2 or intolerable Grade 1 adverse events with the study agent

will be instituted only after the adverse event has been resolved to the satisfaction of the Protocol Principal Investigator. If the Grade 2 or intolerable Grade 1 adverse event recurs after re-challenge, the participant will be withdrawn from the study and followed off study agent for at least 30 days or for the remainder of the planned intervention period (whichever is longer).

## 5.7 Adherence/Compliance

Although drug concentration will not be measured in the blood, compliance will be monitored in the following ways:

*Pill diary completion:* Compliance will be monitored by a pill diary that all participants will be asked to complete (see Appendix B). Participants will be asked to mail back their pill diary and their unused agent supplies after each phone call at Month 3, 6, and 9 visits and to bring both their pill diary and their unused agent supplies to the Post-Intervention evaluation at Month 12 visit.

*Dose count:* Randomized participants will receive their initial 3 month (90 pills plus 10 additional pills) supply of study agent at the randomization visit. At Month 3, 6, and 9 visits the participants will be asked to return all full and empty bottles by mail, and to start taking pills from their new 3 month (90 pills plus 10 additional pills) supply that has been mailed to them. After each visit at Months 3, 6, 9 and 12 compliance will be measured as follows:

number of tablets taken (i.e., number of tablets given - number of tablets returned) / number of tablets that should have been taken during that period of time x100 = % compliance.

Compliance (acceptable adherence to study agent) will be defined as ingestion of  $\geq 80\%$  of the planned agent doses for the purposes of secondary data analyses. In cases where the tablets are not returned, the compliance has to be calculated from the calendar. In cases of non-compliance with the study agent, the participant will be reinstructed. The research nurse or study coordinator and the physicians will provide education for participants, indicating when and how should the tablets be administered.

In case of concomitant medications, subjects are asked to contact the study staff in order to check whether any potential interference is expected. Data on drug suspension or interruption will be reported in the CRFs.

## 6. PHARMACEUTICAL INFORMATION

### 6.1 Study Agent (IND #, IND Sponsor)

This study will not be conducted under an IND.

Aspirin (325 mg enteric coated tablets) and placebo will be supplied by NCI, DCP. Aspirin is an odorless white, needle-like crystalline or powdery substance. When exposed to moisture, aspirin hydrolyzes into salicylic and acetic acids, and gives off a vinegary-odor. It is highly lipid soluble and slightly soluble in water. The 325 mg aspirin tablet contains 325 mg aspirin and the following excipients: carnauba wax, cellulose, D&C Yellow #10 Aluminum Lake, FD&C Yellow #6 Aluminum Lake, hypromellose, iron oxides, methacrylic acid copolymer, polysorbate 80, propylene glycol, shellac, sodium lauryl sulfate, starch, titanium dioxide, triacetin.

#### 6.1.1 Rescue Medication:

Participants will be allowed to take acetaminophen in clinically indicated doses for headache or pain, but will not be allowed to take aspirin or other NSAIDS during the entire study period (baseline to 18 months after randomization).

### 6.2 Reported Adverse Events and Potential Risks

Aspirin has been associated with gastrointestinal (GI) side effects. GI side effects include stomach pain, heartburn, nausea, vomiting, and gross GI bleeding. Minor upper GI symptoms, such as dyspepsia, are common and can occur anytime during therapy. Aspirin has also been associated with an increased risk of hemorrhagic stroke. Aspirin has also been associated with elevated hepatic enzymes, blood urea nitrogen and serum creatinine, hyperkalemia, proteinuria, and prolonged bleeding time. High-dose aspirin has been associated with tinnitus.

### 6.3 Availability

Aspirin and aspirin placebo are investigational agents supplied to investigators by NCI, DCP.

### 6.4 Agent Distribution

Agents will only be released by NCI, DCP after documentation of IRB approval of the DCP-approved protocol and consent is provided to DCP and the collection of all Essential Documents is complete (see DCP website for description of Essential Documents).

NCI, DCP-supplied agents may be requested by the Investigator (or their authorized designees) at each Organization. DCP guidelines require that the agent be shipped directly to the institution or site where the agent will be prepared and administered. DCP does not permit the transfer of agents between institutions (unless prior approval from DCP is obtained). DCP does not automatically ship agents; the site must make a request. Agents are requested by completing the DCP Clinical Drug Request form (NIH-986) (to include complete shipping contact information) and faxing or mailing the form to the DCP agent repository contractor:

[name]  
MRIGlobal  
DCP Chemoprevention Agent Repository  
[name]  
Kansas City, MO 64110  
[contact]  
Emergency [contact]  
Email: [contact]

### 6.5 Agent Accountability

The Investigator, or a responsible party designated by the Investigator, must maintain a careful record of the inventory and disposition of all agents received from DCP using the NCI Drug Accountability Record Form (DARF) or an institutionally-approved accountability system. The Investigator is required to maintain adequate records of receipt, dispensing and final disposition of study agent. Include on receipt record from whom the agent was received and to whom study agent was shipped, date, quantity and batch or lot number. On dispensing record, note quantities and dates study agent was dispensed to and returned by each participant. The protocol site PI(s) or their representative will be responsible for study agent accountability for participants at his/her participating site.

## **6.6 Packaging and Labeling**

Aspirin and aspirin placebo will be packaged by NCI, DCP.

## **6.7 Storage**

Study drug will be stored in a secure location, at controlled room temperature (59°F and 86°F) under low humidity. All agents should be kept in a secured storage area.

## **6.8 Registration/Randomization**

### *Screening and Registration into the DMI Database:*

Once informed consent has been signed, participants will be registered into the DMI database. The DMI database will assign a participant's ID upon completion of the registration process.

### *Randomization:*

Participants will be assigned a randomization number once the following has been accomplished: eligibility has been verified at the site level, eligibility has been confirmed by the site PI, and eligibility CRF has been entered into the DMI web application. The randomization number will be generated by the database and assigned to the participant. Refer to Section 13.2 for details of randomization.

### *Screening/Registration/Randomization into site-specific databases:*

The DMI is the database of record for the study. Registration and randomization should occur per the procedures outlined above. If the site staff need to enter study data into site-specific electronic databases per their institutional requirements, they should do so in accordance with their institutional policies and procedures.

Appropriate CRFs must be completed for any participant who signs an informed consent. If a consented participant is a screen failure and deemed ineligible, the following CRFs must be completed: 1) the Registration CRF; 2) the Randomization CRF with the eligibility box checked "no", 3) the Inclusion and Exclusion CRFs showing why the participant is ineligible, 4) the Off-Study CRF, 5) the Adverse Event CRF, 6) the Concomitant Medication CRF and 7) the Verification CRF. If no Adverse Event and/or Concomitant Medications were assessed by the time the participant is deemed ineligible, the "NONE" box will be checked to complete both CRFs. All participants who sign an informed consent must formally go off study. All participant registration information will be entered into DMI. If a participant experiences a serious adverse event during the screening process, an SAE form must be completed.

## **6.9 Blinding and Unblinding Methods**

- 6.9.1 Participants will be blinded to aspirin or placebo.
- 6.9.2 The Statistician and the Site Study Pharmacist will not be blinded to aspirin or placebo.
- 6.9.3 All other Investigators will be blinded to aspirin or placebo and to the dose level.
- 6.9.4 All participants will take one 325 mg tablet per day of aspirin or an identical-appearing placebo tablet.
- 6.9.5 Study assignments will be unblinded to the Study Investigators and Site Coordinators after all of the data are collected and the study database has been locked. Unblinding will also occur if the participant's physician deems that unblinding is necessary, such as in the case of unacceptable toxicity thought to be related to the study agent or progressive disease, or if the participant becomes pregnant.
- 6.9.6 The Data and Safety Monitoring Board will also be blinded unless unblinding is warranted (if the participant's physician deems that unblinding is necessary, if the

participant becomes pregnant, or after all of the data are collected and the study database has been locked).

- 6.9.7 Unblinding will only take place after consultation with the NCI, DCP Task Order Monitor (Medical Monitor). Unblinding will be conducted as follows:
- 1) The Site PI contacts the Protocol Chairman (the Protocol Principal Investigator) and requests the participant's treatment status be unblinded.
  - 2) The Protocol Chairman (the Protocol Principal Investigator) contacts the NCI, DCP Task Order Monitor (Medical Monitor) and requests the participant's treatment status be unblinded. The Protocol Chairman then conveys the Task Order Monitor's decision to the Site PI. The Site PI then proceeds with unblinding as written out below.
  - 3) If the NCI Task Order Monitor cannot be reached and the participant requires emergency care, the Protocol Chairman (the Protocol Principal Investigator) may authorize the site PI to break the blind.
  - 4) If the Site PI is unable to reach the Protocol Chairman and the participant requires emergency care, then the Site PI must proceed with unblinding as written out below.
  - 5) The Site PI requests the participant's treatment status be unblinded by the research pharmacist (or designated individual responsible for dispensing drug).
  - 6) The Site PI officially takes the participant off-study.
  - 7) The date and reason for breaking the blind must be submitted by the Site PI to the Protocol Chairman, [name], as soon as possible.
  - 8) It is the responsibility of the Study Chairman to report the date and reason for breaking the blind to the **NCI Task Order Monitor**, [name], DO as soon as possible after receiving this information from the Site PI.

NCI Task Order Monitor:

[name], DO, MSc

National Cancer Institute

Division of Cancer Prevention

Gastrointestinal and Other Cancers Research Group

[name]

Rockville, MD 20850

[contact]

Fax (with cover sheet, Attn: [name]): [contact]

Email: [[contact]](mailto:[contact])

- 9) The date and reason for breaking the blind must be submitted by the Study Chairman to the MD Anderson Consortium Principal Investigator, [name], PhD, or designee as soon as possible via email to [[contact]](mailto:[contact]).
- 10) The date and reason for breaking the blind will be reported by the Study Chairman to the MD Anderson DSMB as soon as possible.

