#### 3.3 Intervention Arms

Participants who have successfully completed radiofrequency ablation for BE with or without dysplasia and who have been histologically-confirmed to be free of Barrett's will be randomly assigned to a 12 month intervention with:

Arm A - aspirin 325 mg PO QD

Arm B – aspirin placebo QD

All participants will take proton pump inhibitor in the FDA approved healing dose as clinically

indicated (omeprazole or S-omeprazole 40 mg twice daily, lansoprazole 30 mg twice daily or equivalent).

Participants will continue study agent up to the day of the 12-month endoscopic assessment (see below).

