## 7.2 Baseline Testing/Prestudy Evaluation

### 7.2.1 Screening

Eligible participants will be identified from patients undergoing or who have undergone radiofrequency ablation for BE and are participating in or will participate in an ongoing surveillance program. Potentially eligible participants will be identified through database/charts/clinic lists prior to Baseline Visit. A letter may be mailed to potentially eligible participants introducing the study to the patients. If the Site chooses to utilize a letter, the letter will be signed by the Site PI who is familiar to the patient as the doctor following their medical condition. If the Site PI is not the patient's physician who is treating their BE, the letter will be co-signed by the physician who is familiar to the patient. To facilitate screening, the Study Coordinators are advised to call potential participants and introduce the study over the phone, as well as administer the screening questionnaires. However, the study team may choose to administer the questionnaires in person when the participant is seen at the clinic. Screening to identify potentially eligible participants takes place prior to obtaining Informed Consent. The following questionnaires will be administered during Screening:

- Baseline history assessment questionnaire, to include a review of cancer history and previous medical history, previous surgery, chemotherapy, radiation, and other cancer-directed therapy history, family history, demographic information, including age and race, history of allergies or intolerance to aspirin, aspirin containing products or NSAIDs.
- Symptom Assessment Questionnaire, to include a review of the following symptoms: gastrointestinal bleeding, hematemesis, hematochezia, melena, abdominal pain/cramping, heart burn, irregular heart rate/palpitations, chest pain, shortness of breath, edema, itching, constipation, diarrhea, headache, dizziness, drowsiness, lightheadedness, vertigo, easy bruising/bleeding.
- Use of concomitant medications will be collected.

If the participant is found to be potentially eligible for the study, a Baseline visit will be scheduled.

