- 8.2.6 **Recurrent Barrett's Esophagus** (at 12 and 18 months) will be ascertained completely and accurately. While we will not have sufficient power to assess differences in histological recurrence of BE during the short course of the study, we will examine this as an exploratory secondary endpoint. *This study will generate data designed to lead to the submission of an adequately powered multi-center prospective chemoprevention trial with histologic recurrence of BE after RFA as the clinically relevant primary endpoint.* At all endoscopic examinations after randomization, all raised mucosal lesions, and all flat lesions suspicious for neoplasia, will be biopsied and excised by EMR, their location and size noted, and pathology material reviewed by the study pathology center for confirmation of diagnosis. For each participant, the surface area of recurrent BE will be estimated along with its Prague classification, histological characteristics, and location. A designated study pathologist will review all pathology specimens without knowledge of treatment assignment. Each biopsy

will be classified (using standard criteria) as normal, Barrett's metaplasia, BE with low- or high-grade dysplasia, neoplasia, indefinite for dysplasia, intramucosal or invasive carcinoma.

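### Section 6.9.5 allows the blind to be broken for undefined progressive disease and 6.9.7 step 6 then takes the participant off-study, so Month 18 data can be lost because of outcome

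*Combined protocol and SAP*

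**What the plan says.** Section 6.9.5 provides that "Unblinding will also occur if the participant's physician deems that unblinding is necessary", and offers examples: "such as in the case of unacceptable toxicity thought to be related to the study agent or progressive disease". Pregnancy is a further route. The protocol does not define progressive disease.

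Section 6.9.7 sets the procedure. The Site PI asks the Protocol Chairman, who asks the Medical Monitor and passes back the decision; only emergency care allows this to be bypassed. After the code is broken, step 6 reads "The Site PI officially takes the participant off-study". The date and reason are then reported upward, as far as the DSMB.

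Other sections bear on this:
- Section 3.3: participants are those "histologically-confirmed to be free of Barrett's will be randomly assigned to a 12 month intervention".
- Section 8.2.6: recurrent Barrett's "at 12 and 18 months) will be ascertained completely and accurately". It is an exploratory, unpowered endpoint. Biopsies are classed from normal through metaplasia and dysplasia to carcinoma, by a pathologist who does not know the arm.
- Section 8.3: participants who stop agent, including those who have completed the intervention, continue in follow-up where possible so that endpoint data are collected.
- Section 8.4: the listed off-study reasons include neither unblinding nor recurrence.

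**The concern.** In most trials, progressive disease means worsening of disease present at entry. Here there is none at entry, so whatever the term covers has to be something that 8.2.6 counts as an outcome. The plan therefore names an outcome as an example of when to open the blind, and a separate step then removes that participant from the study.

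The first scheduled endoscopy after randomization is at Month 12, when study agent ends for everyone. A participant unblinded for a finding there would lose the Month 18 CDX2, NF-kB, PGE2, cytokine and recurrence readings. Section 13.4 expects rising CDX2 to accompany metaplasia, so the participants lost would be those expected to have the highest CDX2. If aspirin lowers recurrence, more of them would come from placebo, and the Month 18 contrast would be pulled toward no difference.

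**Working it through.** **1. The text.** Following 6.9.5 and then 6.9.7 step 6, a participant with an 8.2.6 finding can leave the study before Month 18. Following 8.3, the same participant, having completed the intervention, stays in follow-up for endpoint data. Section 8.2.6 requires complete ascertainment at both 12 and 18 months, and 8.4 gives no off-study reason that fits. These sections cannot all be followed for that participant.

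**2. The plan's own figure (13.4).** Difference 20, SD 20, so d = 20/20 = 1.0; 18 per arm; two-sided 5%. The two-sample t-test (noncentral t) gives 83.0%, which reproduces the stated 83%. Enrolment is 18/0.9 = 20 per arm, as stated. This power is for Month 12; the plan states no effect size or power for Month 18.

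**3. How many could meet the trigger.** Section 2.2 gives recurrence of Barrett's after ablation as 8% to 25% in long-term follow-up. Of 40 participants: 40 × 0.08 = 3.2 and 40 × 0.25 = 10. This is an upper-end illustration. It uses the broad reading, treats a long-term rate as if reached within the trial, and assumes that every case is unblinded. The documents give no rate for the narrow reading.

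**4. Bias if losses differ by arm.** Let an arm have mean change μ, and let a fraction p be lost whose mean change is k above those who remain. Then μ = m + pk, so the retained mean is m = μ − pk. Assume placebo μ = 20 and p = 0.25; aspirin μ = 0 and p = 0.08.

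Retained difference = (20 − 0.25k) − (0 − 0.08k) = 20 − 0.17k.

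- k = 20 (1 SD): 20 − 3.4 = 16.6
- k = 40 (2 SD): 20 − 6.8 = 13.2

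**5. A second model.** Suppose that those lost are exactly the highest changes in each arm, normally distributed with SD 20. With a fraction r lost, the retained mean is μ − 20φ(z)/(1 − r), where z cuts off the top r. With aspirin recurrence half that on placebo:

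| Lost, placebo v aspirin | Retained difference |
|---|---|
| 8% v 4% | 18.6 |
| 25% v 12.5% | 16.2 |

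The direction is the same as in step 4.

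**6. Equal losses.** If the same fraction is lost in both arms with the same excess, the difference stays at 20 and only precision suffers. At 25%, 18 × 0.75 = 13.5 per arm, and power at d = 1.0 falls from 83.0% to 70.4%. The 10% attrition allowance does not cover a loss of that size.

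**7. Source of these figures.** Every number in steps 4 to 6 comes from participants leaving the study. If step 6 of 6.9.7 did not remove them, none of these losses would arise.

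**The case against.** The other side has a good deal, and several stronger readings that a reader might infer fail because of it.

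- **That progressive disease simply is the recurrence endpoint.** The text never says so. Sections 2.1 and 2.2 use progression for neoplastic change and recurrence for the return of Barrett's, so the term may mean only dysplasia or cancer. Those are still 8.2.6 categories, so the conflict survives, but the 8% to 25% range then does not apply.
- **That an endpoint finding opens the blind as a matter of course.** It does not. A physician must judge unblinding necessary and, outside an emergency, the Medical Monitor is consulted first. With study agent ending at Month 12, approval may be uncommon. However, 6.9.7 gives no criterion for refusal, and 6.9.5 itself names the example.
- **That the primary endpoint is compromised.** A recurrence found at the Month 12 endoscopy comes with the research biopsies taken at the same procedure. Only a finding at an unscheduled endoscopy before Month 12, followed by unblinding, would cost primary data.
- **That Month 18 recurrence would be judged by someone who knows the arm.** Section 7.2.1 describes a recruitment letter "signed by the Site PI who is familiar to the patient as the doctor following their medical condition", but it also allows that the Site PI is not the treating physician, and the plan does not say that the Site PI performs the Month 18 endoscopy. Biopsy sites are prescribed, and 8.2.6 leaves little choice over lesions: "At all endoscopic examinations after randomization, all raised mucosal lesions, and all flat lesions suspicious for neoplasia, will be biopsied and excised by EMR". The pathologist and laboratories are blinded. Anyone unblinded for a Month 12 recurrence already has that event recorded.

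The arm may also matter to a physician managing a lesion, which is a reason not to bar unblinding outright. What stands is the sequence from an outcome finding, through a code break, to removal from the study.

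**Conclusion.** The plan contradicts itself on whether a participant unblinded for an outcome finding remains in follow-up. As written, 6.9.5 with 6.9.7 step 6 permits Month 18 data to be lost because of outcome, possibly differently by arm. The exposure is confined mainly to the Month 18 secondary biomarkers and the exploratory recurrence endpoint.

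The size is not known. The range of 16.6 to 13.2 for a 20-unit difference depends on four assumptions: arm loss rates of 25% and 8%, taken from the two ends of a long-term recurrence range; every such case being unblinded and removed; a CDX2 excess of 20 to 40 units that the documents do not supply; and a Month 12 effect carried over to Month 18, six months after agent stops. With equal losses there is no such bias, only less precision. The contradiction itself rests on none of these assumptions.

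**What to change.** Reconcile 6.9.5 and 6.9.7 step 6 with 8.2.6, 8.3 and 8.4:

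1. In 6.9.5, remove progressive disease as a stand-alone example and state that an 8.2.6 endpoint finding is not by itself a reason to break the blind. Leave the physician-necessity, emergency and pregnancy routes and the Medical Monitor consultation as they are.
2. In 6.9.7, provide that a participant unblinded for an endpoint finding stays in follow-up through Month 18, in line with 8.3.
3. Report unblindings by arm, date and reason.

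The cost is a short amendment. The downside is that a physician managing a recurrence would usually learn the arm only after database lock, unless unblinding is judged necessary for care. Both text changes are needed: the second alone saves the data but leaves an outcome as a named reason to unblind, and the first alone leaves removal in place for anyone who is still unblinded after such a finding.
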